1.2.7. Study Rationale

This will be 1 of 2 studies (B1971035 and B1971017) that will together explore the immunogenicity and safety of bivalent rLP2086 in toddlers and children aged 12 months to 10 years.

This 2-stage study (B1971035) will seek to evaluate the safety, tolerability, and immunogenicity of bivalent rLP2086 at 2 dose levels (60 μ g and 120 μ g) in healthy toddlers aged 12 to <24 months. Stage 1 will be composed of a sentinel-enrollment phase with 2 sentinel cohorts and an expanded-enrollment phase. Selection of dose level for the expanded-enrollment phase will be based on an internal review committee (IRC) review of the safety profile of the 2 dose levels.

- Should the IRC determine that safety data for both dose levels demonstrate a satisfactory safety profile, the 120-µg dose level will be selected for the expanded-enrollment phase.
- Should the IRC determine that safety data for the 60-µg dose level demonstrate a satisfactory safety profile, and the 120-µg dose level does not demonstrate a satisfactory safety profile, the 60-µg dose level will be selected for the expanded-enrollment phase.

Stage 2 will assess the duration of the immune response.

Risks/Benefits

Complete information on risks/benefits for this compound may be found in the SRSD, which for this study is the most recent version of the bivalent rLP2086 IB.

Refer to the most recent version of the licensed pediatric HAV vaccine USPI for a summary of the known and potential risks and benefits, if any, to human subjects.

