If the IRC determines that vaccination should not proceed with the 120-µg dose level, the 120-µg sentinel cohort will be discontinued and no further investigational product will be administered for this age cohort at the 120-µg dose level. However, follow-up procedures will be performed as described in Section 6.1.11.

Final Protocol Amendment 2, 19 April 2016

A summary of the 120-µg sentinel-cohort enrollment and progression for subjects aged 12 to <15 months is illustrated in Table 2.

Table 2. 120-µg Sentinel Cohort, Aged 12 to <15 Months, Enrollment and Progress

	Visit 1	Is Safety Review Acceptable?	Visit 4	Visit 6	Sentinel-Cohort Progression
120 μg	Administer Vaccination 1 ^a	YES	Administer Vaccination 2		All subjects who received the 3-vaccination series of 120 µg of bivalent rLP2086 progress to Stage 2 (Visits 11-13). Subjects who received the 3-vaccination series of HAV vaccine/saline complete the study at Visit 10.
		NO	Discontinue 120-µg sentinel cohort – no further investigational product will be given to these subjects. See Section 6.1.11 for follow-up procedures.		

a. Staggered enrollment applies (see Section 3.3.2).

Abbreviation: HAV = hepatitis A virus.

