8.1.2.2. Safety Data

All of the safety endpoints (including reactogenicity data and (S)AE) will be summarized with percentages and 95% exact CI for each group.

The safety data will be compared between rLP2086 (by dose) and control group as below:

- The percentages of subjects reporting immediate AEs, reporting reactogenicity events (including use of antipyretic medication) will be compared with unconditional exact test (Chan & Zhang, 1999)⁵ for the pair-wise comparisons. The 95% exact CIs on the difference will be also provided. The exact CIs will be computed using the noninferiority procedure, using the standardized test statistic and $\gamma=0.000001$.
- Fisher's exact test will be used to compare the percentage of subjects reporting (S)AE, MAEs, and NDCMCs. The difference in the percentages between rLP2086 (by dose) and control group and 2 sided 95% CIs for the difference will be provided. The CIs of the difference will be computed using the Miettinen-Nurminen⁶ method.

The confidence intervals and statistical tests presented for the safety data will not be used to test hypotheses but will be used to determine which events may need further clinical investigation. No adjustment for multiplicity is needed.

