8.2.5. Analysis of Safety Data

Similar to the immunogenicity analysis, the control group and each dose-level group from different cohorts within the same age stratum will be pooled for analysis. All of the safety analyses will be summarized for each age stratum separately as well as for the overall populations. The summaries combining age cohorts will only be provided if the same dose-level is chosen for the expanded enrolment for each cohort. If there are no events for a specific safety analysis for the combined age strata, summaries by each age strata may not be performed.

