8.2.5.1. Reactogenicity Data

The derived variables for the presence of each local reaction, each systemic event, fever, and use of antipyretic medication at each day and ‘any day 1-7’, and any local reaction and any systemic events at ‘any day 1-7’ will be summarized with number and proportion of subjects reporting such event, for each vaccination. The presence of each local reaction, each systemic event, fever, use of antipyretic medication, any local reaction, any systemic events will also be summarized for ‘any day 1-7’ after any vaccination similarly. The summaries will include 95% CIs. Clopper-Pearson’s method will be used to calculate the 95% CI.

The maximum severity of each local reaction, systemic events, and fever at ‘any day 1-7’ will be summarized with number and proportion of subjects reporting such maximum severity of the event, by each vaccination as well as ‘after any vaccination’. The summaries will include 95% Clopper-Pearson’s CI.

For local reactions and systemic events, including fever and use of antipyretic medication, the maximum duration of the event will be summarized for each vaccination. The number of unknown durations will also be summarized. The onset day for each local reaction and systemic event will also be summarized.

All of these summaries will be summarized according to the vaccine received. The safety population at each corresponding dose will be used for the analyses for each vaccination.

The data summaries will be descriptively presented by group.

Proportion differences (between rLP2086 dose groups and HAV/saline control group), associated 95% CIs and p-values will only be provided, by each vaccination and after any vaccination for the following endpoints:

- any local reactions (overall and by type of event) and any severe local reactions (only by type of event)
- any systemic events (overall and by type of event) and severe systemic events (only by type of event)
- any use of anti-pyretics
- any fever ($\geq 38.0^{\circ}\text{C}$) and also any temperature above or equal to 39.0-39.9, and 40 degrees centigrade.

P-values from the comparison and 95% exact CIs on the difference will be computed using the noninferiority procedure, using the standardized test statistic and $\gamma=0.000001$.

Also, the increasing severity and potentiation of local and systemic reactions across all 3 vaccinations will be summarized with number and proportion of subjects with such characteristics, along with 95% exact CI.

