8.2.7. Subgroup Analysis

Some immunogenicity and safety endpoints will be descriptively summarized by race, by gender, and by country, and within age strata as described in [Section 6.4](#).

All of the safety and immunogenicity analyses will be summarized for each age stratum separately as well as for the overall populations. Note that for both the immunogenicity and the safety summaries, the summaries combining age cohorts will only be provided if the same dose-level is chosen for the expanded enrolment for each cohort. For example, if the low dose is chosen in the 12-18 months old age cohort and the high dose is chosen for the 18-24 months old age cohort, then the safety and immunogenicity results for the 12-24 months old group combined will not be presented. If there are no events for a specific safety analysis for the combined age strata, summaries by each age strata may not be performed.

For the safety endpoints (AE, SAE collected, medically attended AE and newly diagnosed chronic medical conditions) collected, a separate summary table including analysis interval of 'Vaccination period', 'Follow-up Phase (Stage 1)' (excluding AEs) and 'Throughout the AE collection period' (excluding AEs), will be provided for the subjects who completed the full series (3 doses) and those who only completed partial series (1 or 2 doses). Similar subgroup analysis will also be provided for those safety endpoints with relatedness of vaccination phase.

All of the p-values and 95% CI provided for the subgroup analyses are considered as descriptive and no multiplicity adjustment will be made on these analyses. No formal inferences will be made between the subgroups.

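### For the dose not expanded, the pooled safety controls are mostly from other cohorts; if 120 µg is stopped after Vaccination 1, the any-vaccination reactogenicity difference is also unmatched on number of injections

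*SAP*

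**What the plan says.** Within each age stratum the Protocol (3.2 to 3.5) plans three separately randomised 2:1 cohorts, opened in sequence: a 60-µg sentinel cohort of about 33, a 120-µg sentinel cohort of about 33, and an expanded cohort of about 132 at one selected dose. Under Protocol 1.2.7, 120 µg is expanded if both doses are satisfactory, and 60 µg if only 60 µg is. If 120 µg is not acceptable after the Vaccination 1 review, the whole sentinel cohort is discontinued and "no further investigational product will be given to these subjects" (Protocol 3.3.2, Table 2; likewise 3.4.2, Table 4). That includes the cohort's controls.

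For safety, "the control group and each dose-level group from different cohorts within the same age stratum will be pooled for analysis" (SAP 8.2.5; also Protocol 9.2 and SAP 6.4). SAP 8.1.2.2 states: "The safety data will be compared between rLP2086 (by dose) and control group as below". For reactogenicity, differences with "associated 95% CIs and p-values will only be provided, by each vaccination and after any vaccination for the following endpoints" (SAP 8.2.5.1). The any-vaccination row uses the overall safety population (SAP Table 3). The intervals and tests are descriptive, but they "will be used to determine which events may need further clinical investigation" (SAP 8.1.2.2).

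Across ages, "The summaries combining age cohorts will only be provided if the same dose-level is chosen for the expanded enrolment for each cohort" (SAP 8.2.5). SAP 8.2.7 tabulates AE, SAE, MAE and NDCMC separately for full and partial series, and SAP 8.2.5.2.7 gives annualised rates for the same four. Neither covers reactogenicity.

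**The concern.** Randomisation protects a comparison between children randomised in the same cohort. Pooling the controls sets the dose not expanded mostly against controls from other cohorts. That matters in two situations.

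(B), the main one: 120 µg is stopped after Vaccination 1. Its recipients and their own controls have one injection, while the other pooled controls are scheduled for three. An endpoint of the form at least one reaction after any vaccination rises with the number of injections, so the difference is pulled down with no cohort drift at all. A dose stopped for its safety profile would be reported as closer to control than it was.

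(A), secondary: 60 µg completes its series but is not expanded. Exposure is then equal, and the worry is only that background rates differ between earlier and later cohorts.

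These are the planned comparisons for the primary safety objective (Protocol 2.1.2), so a missed or false signal is the cost.

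**Working it through.** **Head count.** At 2:1, 33 = 22 + 11 and 132 = 88 + 44. The total is 2 × (33 + 33 + 132) = 396, or 264 vaccine and 132 control, as in Protocol 3.9 and SAP 2.1.5. The selected dose has 22 + 88 = 110 per stratum, as in Protocol 9.1. Controls per stratum are 11 + 11 + 44 = 66. For the dose not expanded, 55/66 = 83% were not randomised with it. For the selected dose only 11/66 = 17% come from the other sentinel cohort.

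**(B) Expected any-vaccination difference with no vaccine effect.** The documents give no reaction rates, so these are assumptions. Let p be the reaction rate per HAV injection and q the chance that a control with the full series reacts at least once. The pooled control rate is (11p + 55q)/66, so the difference is p - (11p + 55q)/66 = -(55/66)(q - p).

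Controls receive HAV, saline, HAV (Protocol Table 6). Two bounds are used for saline: it reacts at the HAV rate, or not at all. With independent injections q = 1 - (1-p)³ or 1 - (1-p)². With correlation 0.5 (beta-binomial) q = 1 - (1-p)(2-p)(3-p)/6 or 1 - (1-p)(2-p)/2.

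| p | saline as HAV, corr. 0 | saline as HAV, corr. 0.5 | no saline reactions, corr. 0 | no saline reactions, corr. 0.5 |
|---|---|---|---|---|
| 10% | -14.2 | -6.1 | -7.5 | -3.8 |
| 20% | -24.0 | -10.7 | -13.3 | -6.7 |
| 30% | -29.8 | -13.7 | -17.5 | -8.8 |

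Example: p = 20%, saline as HAV, independent: q = 48.8%, and -(55/66) × 28.8 = -24.0 points.

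The chance that the unconditional exact test flags fewer events on vaccine (nominal 2.5%) at p = 10%, 20%, 30% is 28%, 52%, 67% in the first column and 4.5%, 8%, 9.5% in the last.

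**(B) With a real excess.** Take 50% v 20% after Vaccination 1, a true difference of 30 points. The pooled any-vaccination control rate at p = 20% is 44.0%, 30.7%, 33.3% or 26.7% in the order of the columns. The any-vaccination difference is therefore +6.0, +19.3, +16.7 or +23.3 points. It is flagged in 6% to 46% of trials. The pooled Vaccination 1 comparison (22 v 66, one injection each) flags it in 71%, and the cohort's own 22 v 11 in 35%.

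**(B) Combined ages.** The younger 120-µg cohort cannot open until 120 µg is accepted in the older one (Protocol 3.3.2). If 120 µg is stopped in the older stratum, controls are 66 older plus 11 + 44 = 55 younger, or 121. The combined table sets 22 recipients against 121 controls, of whom 110 (91%) were not randomised with them. If 120 µg is stopped only in the younger stratum and expanded in the older, the selected doses differ and no combined table is produced.

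**(A).** With no vaccine effect and an assumed 10-point drift between the 60-µg cohort and the later ones, the difference shifts by 10 × 55/66 = 8.3 points. Fisher flags go from 4.2% (all rates 50%) to 8.8% (60% v 50%). In the younger stratum 22 of 66 controls are 15 to <18 months against none of the 60-µg group. An assumed 10-point age effect shifts the difference by only 10 × 22/66 = 3.3 points (flags 4.7% v 4.0%).

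**Precision of an own-control difference.** The half-width at 50% is 1.96 × √(0.25/a + 0.25/b): 36 points for 22 v 11 against 24 for 22 v 66, and 26 for 44 v 22 against 17 for 44 v 132.

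**The case against.** The strongest reply is that the plan already has the right comparison. Reactogenicity differences are planned by each vaccination, and after Vaccination 1 all 22 + 66 children have had one injection. That comparison has more power than the own-cohort one (71% v 35% above). AE, SAE, MAE and NDCMC have the full/partial-series tables and annualised rates. All of this stands, and it confines the gap mainly to the any-vaccination reactogenicity difference. It does not correct that difference. The series tables are not defined by cohort, and the annualised rates standardise for days on study, not for injections.

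It is also fair that the figures in (B) depend on how reactogenic saline is, which is why the range extends to no saline reactions. The direction does not change. The bias vanishes only if the extra injections add no child who would not already have reacted.

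For (A), no passage suggests drift between cohorts; the shift is conditional on an assumption.

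A reader might infer more than the documents support:
- That dose escalation or dose selection is compromised. The internal review committee works from each sentinel cohort's own 7-day data after Vaccination 1 (Protocol 3.2.1, 9.4.1).
- That 83% of controls from other cohorts is itself evidence of bias. In (A) it is not, without drift.
- That no within-cohort difference will exist anywhere. The SAP text plans none, but mock tables are prepared separately (SAP 2) and the committee charter is not among the documents.

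**Conclusion.** The point holds in limited form, as a cheap improvement. For the dose not expanded, 83% of the pooled controls per stratum were randomised elsewhere. If 120 µg is stopped after Vaccination 1, the planned any-vaccination reactogenicity difference is biased in favour of the stopped dose. With no vaccine effect the size is -14.2 to -3.8, -24.0 to -6.7 or -29.8 to -8.8 points at 10%, 20% or 30% per HAV injection. A true 30-point excess (50% v 20%) would appear as +6.0 to +23.3.

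These ranges assume correlation between injections of 0 to 0.5, saline reacting from the HAV rate down to not at all, no drift, and all 55 other controls completing three injections. (A) is secondary and rests on assumed drift. The selected dose is little affected.

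**What to change.** Keep the pooled comparison of Protocol 9.2. In SAP 8.1.2.2, 8.2.5 and 8.2.5.1, for the dose not expanded only:

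- Beside each planned difference, add the difference and 95% CI against that cohort's own controls by the planned method: 22 v 11 per stratum.
- In the combined-age table, use 44 v 22 stratified by age in (A) only. Name the interval (Miettinen-Nurminen or another stratified form), because no stratified form of the Chan-Zhang interval is specified. In (B), when only the older 120-µg cohort exists, use 22 v 11.
- Footnote the pooled any-vaccination, vaccination-phase and Visit 1 to Visit 8 differences for a stopped cohort as having unequal numbers of vaccinations, and point to the Vaccination 1 comparison as the exposure-matched screen.
- State that the own-control difference is the randomised estimate, and that it neither confirms nor clears a flag.

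The cost is SAP wording, a footnote, and extra columns across the reactogenicity and AE tables for one dose group. The added interval is wide, about 36 points half-width per stratum at 50%, so it supplements the pooled screen and does not replace it.

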8.2.5.1. Reactogenicity Data

The derived variables for the presence of each local reaction, each systemic event, fever, and use of antipyretic medication at each day and ‘any day 1-7’, and any local reaction and any systemic events at ‘any day 1-7’ will be summarized with number and proportion of subjects reporting such event, for each vaccination. The presence of each local reaction, each systemic event, fever, use of antipyretic medication, any local reaction, any systemic events will also be summarized for ‘any day 1-7’ after any vaccination similarly. The summaries will include 95% CIs. Clopper-Pearson’s method will be used to calculate the 95% CI.

The maximum severity of each local reaction, systemic events, and fever at ‘any day 1-7’ will be summarized with number and proportion of subjects reporting such maximum severity of the event, by each vaccination as well as ‘after any vaccination’. The summaries will include 95% Clopper-Pearson’s CI.

For local reactions and systemic events, including fever and use of antipyretic medication, the maximum duration of the event will be summarized for each vaccination. The number of unknown durations will also be summarized. The onset day for each local reaction and systemic event will also be summarized.

All of these summaries will be summarized according to the vaccine received. The safety population at each corresponding dose will be used for the analyses for each vaccination.

The data summaries will be descriptively presented by group.

Proportion differences (between rLP2086 dose groups and HAV/saline control group), associated 95% CIs and p-values will only be provided, by each vaccination and after any vaccination for the following endpoints:

- any local reactions (overall and by type of event) and any severe local reactions (only by type of event)
- any systemic events (overall and by type of event) and severe systemic events (only by type of event)
- any use of anti-pyretics
- any fever ($\geq 38.0^{\circ}\text{C}$) and also any temperature above or equal to 39.0-39.9, and 40 degrees centigrade.

P-values from the comparison and 95% exact CIs on the difference will be computed using the noninferiority procedure, using the standardized test statistic and $\gamma=0.000001$.

Also, the increasing severity and potentiation of local and systemic reactions across all 3 vaccinations will be summarized with number and proportion of subjects with such characteristics, along with 95% exact CI.

A listing will be provided for all of the severe reactogenicity data.

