2.1. Study Design

2.1.1. Description

The study is a Phase 2, randomized, active-controlled, observer-blinded, sponsor-unblinded, multicenter study in which approximately 396 healthy toddlers stratified by age, 12 to <18 months or 18 to <24 months old, will be randomly assigned in a 2:1 ratio to receive either 1 of 2 dose levels (60 µg or 120 µg) of bivalent rLP2086 or HAV a licensed pediatric vaccine /sterile saline solution for injection (0.85% sodium chloride) in a 0.5-mL dose.

The study will be conducted in 2 stages:

Stage 1 will assess vaccine immunogenicity, safety, and tolerability across 2 phases: a sentinel-enrollment phase and an expanded-enrollment phase. Within the sentinel-enrollment phase, 2 sentinel cohorts will be enrolled: one composed of subjects aged 12 to <15 months and the other of subjects aged 18 to <24 months. The expanded-enrollment phase will be open to subjects in 2 cohorts, one aged 12 to <18 months and the other aged 18 to <24 months.

Within the study age cohort of 12 to <18 months, an additional subset of subjects aged 12 to <15 months is identified for the sentinel phase of the study. The designation of a subset of subjects aged 12 to <15 months aims to ensure that the sentinel cohort includes adequate enrollment of this youngest age cohort to support assessment of post-vaccination reactions and AEs prior to the start of enrollment of the expanded-enrollment phase.

Stage 2 will assess the duration of the immune response to bivalent rLP2086; hence, only those subjects randomly assigned to bivalent rLP2086 (irrespective of dose level) will be eligible for Stage 2.

Bivalent rLP2086 will be administered on a Month 0, 2, and 6 schedule.

HAV vaccine is administered at Months 0 and 6 and has been selected as the vaccine control so that subjects randomly assigned to the control group receive a benefit from participating in the study. HAV vaccine has a well-established tolerability profile and will provide protection to subjects who may become at increased risk for hepatitis A viral infection either during future travel or during other exposures. As the recommended schedule for HAV vaccine is 2 doses 6 months apart, saline will be given at Month 2 to maintain the study blind.

2.1.2. Sentinel- and Expanded-Enrollment Plan, Stage 1

2.1.2.1. Sentinel Enrollment, Stage 1

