6.2.2.1. Local Reactions Endpoints

The local reactions collected from the e-Diary will be: tenderness at injection site, redness, and swelling.

Local Reaction Presence (Proportion of subjects reporting each local reaction)

For each local reaction, the derivation of whether or not the specific reaction occurred on each day and ‘any day 1-7’ will be made. The variable will be calculated for each vaccination as well as overall reactions for any vaccination. The derivation of this variable is given in Table 4 below.

Table 4. Derived Variables for Local Reactions

Variable	Yes (1) ^a	No (0) ^b	Missing (.)
Any day 1-7	Parent/legal guardian reports the reaction as ‘mild’ ‘moderate’ or ‘severe’ on any day 1-7	Parent/legal guardian reports the reaction as ‘none’ on all 7 days or as a combination of ‘none’ and missing on all 7 days.	Parent/legal guardian reports the reaction as missing on all 7 days.

- a. For redness and swelling, ‘mild’, moderate’, and ‘severe’ categories were based on the caliper size reported from e-Diary
- b. For redness and swelling, ‘none’ means 0 caliper units reported in the e-Diary

Maximum Severity for Local Reaction

A caliper is used to measure the redness or swelling area. Caliper units are converted to centimeters according to 1 caliper unit = 0.5 centimeters. The grading of local reactions is listed below in Table 5 and Table 6.

Table 5. Grading of Redness and Swelling

Grades	Measurement
None	0 cm (0 caliper units)
Mild	0.5 to 2.0 cm (1 to 4 caliper units)
Moderate	2.5 to 7.0 cm (5 to 14 caliper units)
Severe	>7.0 cm (>14 caliper units)

Table 6. Grading of Tenderness

Grades	
Mild	Hurts if gently touched (eg, subject whimpers, winces, protests, or withdraws)
Moderate	Hurts if gently touched with crying
Severe	Causes limitation of limb movement

The maximum severity (highest grading) of each local reaction within 7 days of vaccination will be derived for each vaccination as well as any vaccinations. The maximum severity will be derived as follows:

= •, if values are missing for all days 1-7;

= 0, if the subject reports all reactions as ‘None’ or a combination of missing and none for all days 1-7

= *highest grade* (maximum severity) within 7 days of vaccination, if the answer is not ‘None’ for at least 1 day;

Duration of Each Local Reaction

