For subjects experiencing any local reactions (or those with derived reaction presence in Table 4), the maximum duration (last day of reaction –first day of reaction +1) will be derived for each vaccination. Resolution of the event is the last day in which the event is recorded in the e-Diary or the date the event ends if it is unresolved during the subject diary-recording period, unless chronicity is established.

In summary, the following variables will be derived for local reaction:

1. Each local reaction on each day (up to day 7) after each vaccination.
2. Each local reaction on ‘any day 1-7’ after each vaccination and any vaccination.
3. Maximum severity of each local reaction on ‘any day 1-7’ after each vaccination and any vaccination.
4. Maximum duration of each local reaction after each vaccination.
5. Any local reaction on ‘any day 1-7’ after each vaccination and after any vaccination.

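### The potentiation summary is an undefined one-way proportion with no count of decreases, so chance rises in severity cannot be separated from real ones

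*SAP*

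**What the plan says.** After the per-dose reactogenicity tables, SAP 8.2.5.1 adds one sentence on change over the series: "the increasing severity and potentiation of local and systemic reactions across all 3 vaccinations will be summarized with number and proportion of subjects". The same sentence attaches a Clopper-Pearson type interval to that proportion, and nothing further describes the measure.

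- **Definition.** SAP 6.2.2.1 closes with a list introduced by "In summary, the following variables will be derived for local reaction". It covers presence by day, presence on any of days 1–7, maximum severity, duration and any reaction. It has no variable for increase or potentiation, and neither does the parallel list in 6.2.2.2.
- **Building block.** The ingredient for a within-child measure exists: "The maximum severity (highest grading) of each local reaction within 7 days of vaccination will be derived for each vaccination".
- **Per-dose tables.** Section 8.2.5.1 also gives "number and proportion of subjects reporting such maximum severity of the event, by each vaccination as well as" pooled over the series, with Clopper-Pearson intervals.
- **Arms.** "The data summaries will be descriptively presented by group". Between-arm statistics are confined to a closed list: "Proportion differences (between rLP2086 dose groups and HAV/saline control group), associated 95% CIs and p-values will only be provided, by each vaccination". The list, which also applies to the series as a whole, covers any and severe local reactions, any and severe systemic events, antipyretic use and fever. Potentiation is not on it.
- **Control regimen.** Controls receive HAV vaccine at Months 0 and 6; "saline will be given at Month 2 to maintain the study blind" (SAP 2.1.1; Protocol 3.1 and Table 6).

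**The concern.** A child's maximum grade over seven days varies from one dose to the next without any change in how reactogenic the vaccine is. Some children will therefore score higher later in the series, and about as many will score lower. A count of the first group alone has no natural reference value: zero is not what one expects under no potentiation, and the exact interval describes sampling error only.

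A reader would look to the control arm for a reference. There, dose 2 is saline between two HAV doses, so severity will tend to fall at the first step and rise at the second by design.

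At stake is whether the one planned within-child summary of repeat-dose reactogenicity can be interpreted at all. Because the definition is open, its expected value under no effect could be anything from under 1% to more than half of the children, depending on a choice the SAP text does not fix.

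**Working it through.** **Inputs.** The documents give no expected reaction rates, no within-child correlation and no figure for potentiation, so there is no plan figure to reproduce. From the documents come the four grades (none, mild, moderate, severe; SAP Tables 5–7), the control sequence HAV–saline–HAV, and 110 subjects in a selected dose and age stratum (Protocol 9.1). The following are assumptions:

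- Grade distributions (none/mild/moderate/severe), identical at all three doses so that there is no true potentiation: 10% rate = 0.90/0.07/0.025/0.005; 50% rate = 0.50/0.28/0.18/0.04; 80% rate = 0.20/0.30/0.40/0.10.
- Latent normal severity with within-child correlation 0 to 0.7 (400,000 simulated children per setting).

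**Step 1: exact check under independence.** With the same distribution p at both doses, P(higher at dose 3 than dose 1) = P(lower) = (1 − Σp²)/2.

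- 50% rate: Σp² = 0.25 + 0.0784 + 0.0324 + 0.0016 = 0.3624, so (1 − 0.3624)/2 = 31.9%.
- 10% rate: Σp² = 0.81 + 0.0049 + 0.000625 + 0.000025 = 0.81555, so (1 − 0.81555)/2 = 9.2%.
- Strict rise at both steps, 50% rate: sum of p_i·p_j·p_k over i<j<k = 0.0252 + 0.0056 + 0.0036 + 0.0020 = 3.6%.

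**Step 2: chance proportions over correlation 0 to 0.7.**

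| Candidate definition | 10% rate | 50% rate | 80% rate |
|---|---|---|---|
| Dose 3 higher than dose 1 | 6.4–9.3% | 21.2–31.8% | 24.0–35.0% |
| Any step up between consecutive doses | 12.4–18.2% | 41.1–60.0% | 46.8–64.9% |
| A rise with no fall over the series | 5.7–8.9% | 18.4–24.5% | 21.4–25.0% |
| Strict rise at both steps | 0.2–0.4% | 1.4–3.6% | 1.3–4.9% |

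In every setting the share lower at dose 3 than at dose 1 equals the share higher, within simulation error.

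**Step 3: what the planned interval would show.** At the 50% rate and correlation 0.5, 25.3% are higher at dose 3. In 110 children that is about 28, and 28/110 = 25.5% with Clopper-Pearson limits 17.6–34.6%. The interval lies far from zero although no potentiation was built in.

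**Step 4: the control arm.** Assume any reaction in 50% after HAV and 25% after saline, correlation 0.5, HAV reactogenicity unchanged between doses.

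| Step | HAV–saline–HAV: share higher | Same product three times: share higher |
|---|---|---|
| Dose 1 to 2 | 8.3% | 25.4% |
| Dose 2 to 3 | 38.9% | 25.3% |
| Dose 1 to 3 | 25.3% | 25.3% |

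With assumed rates of 30% and 15%, and correlation 0 to 0.7, the first two steps give 5–11% and 23–27%. Both steps involving dose 2 are distorted; dose 1 to 3 is not.

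**Step 5: what a net figure would do.** At the 50% rate and correlation 0.5, dose 1 to 3 gives 25.3% higher minus 25.3% lower = 0. If the any-reaction rate truly rises 40%, 50%, 60% over the three doses, it gives 39.3% higher minus 14.3% lower = +25.0 points. The one-way figure moves from 25.3% to 39.3% with nothing to show where chance ends.

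**The case against.** A reader might infer three stronger things that the documents do not support.

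- **That the increase proportion is the only evidence on change across doses.** It is not. The same section tabulates presence and maximum severity of each reaction per vaccination and by group, with intervals, and lists severe reactions. A group-level shift, including a decline, would be visible there. For presence versus absence in a fixed set of children, higher minus lower equals the difference between the two per-dose proportions, so that point value is nearly available already. What those tables lack is within-child change in grade and an interval for the change. They also use the safety population of each vaccination (SAP 5.3), so the children can differ between doses.
- **That the control arm cannot serve as a reference.** Doses 1 and 3 are both HAV, so that contrast is free of the saline problem. The SAP simply does not plan it. Nor does it plan any formal between-arm statistic for potentiation, although the by-group display puts the arms side by side.
- **That the chance proportion is large whatever the definition.** A strict rise at both steps is a fair reading of a change across all three vaccinations. By chance it reaches about 5% at most, and rare reactions give under 10% for dose 3 against dose 1.

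It can also be said that mock-up tables and programming rules are kept separately (SAP Section 2) and may hold a definition. Further, potentiation is not among the primary safety endpoints (Protocol 2.2.2; SAP 6.2.1), and the study is descriptive (SAP 4.1). These points lower the importance. They do not make an undefined one-way count readable, and safety intervals are still meant to flag events for clinical follow-up (SAP 8.1.2.2).

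**Conclusion.** The point holds as a minor one. As written, the potentiation summary is undefined and counts change in one direction. For most natural definitions its value with no potentiation is well above zero: 21–32% for dose 3 against dose 1 at an assumed 50% rate, with as many children lower, and about 6–9% at an assumed 10% rate. For a strict rise at both steps it is about 1–4% at the 50% rate. The per-dose severity tables partly cover the gap at group level. Control-arm changes that involve dose 2 mainly reflect saline; dose 1 to 3 is the usable contrast.

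The percentages rest on assumed grade distributions, a latent-normal correlation of 0 to 0.7 and a four-grade scale. They do not describe fever, which has five temperature bands (SAP 6.2.2.3). The equality of rises and falls when the grade distribution is the same at each dose does not depend on the particular rates.

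**What to change.** Amend SAP 8.2.5.1, with a matching entry in the variable lists of 6.2.2.1 to 6.2.2.3:

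1. Define the potentiation variable from maximum grade per vaccination.
2. For children with diary data at both doses, report the number with a higher and the number with a lower maximum grade for dose 1 to 2, 2 to 3 and 1 to 3.
3. Give the paired difference (higher minus lower) with a named interval for a difference in paired proportions, for example an exact unconditional, Newcombe or Tango interval. If a p-value is shown, use the exact McNemar test; that test conditions on the discordant pairs and does not itself supply the interval.
4. Compare arms descriptively for dose 1 to 3 only, using the net difference. It is zero under no change in either arm, whereas the one-way share depends on each product's reaction rate.
5. Footnote that control changes involving dose 2 reflect saline.

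No new data are needed, because maximum severity per vaccination is already derived. The cost is some SAP wording and a longer table: three contrasts for each reaction, by dose group and age stratum.
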